**PROTOCOL SUMMARY**

**Study Title:** Open Label, Phase II Trial Of Neoadjuvant TAK-228 Plus Tamoxifen In Patients With Estrogen Receptor (ER)-Positive, Human Epidermal Growth Factor Receptor Type 2 (HER2)-Negative Breast Cancer

**Phase:** II

**Number of Patients:** 35

**Study Objectives:**

Primary

- To evaluate Ki67 before and after treatment with the mammalian target of rapamycin complex (mTORC) 1 and 2 inhibitor TAK-228 plus the non-steroidal agent tamoxifen in patients with newly diagnosed ER-positive, HER2-negative breast cancer.

Secondary

- To evaluate the pathological complete response (pCR) rate after treatment with TAK-228 plus tamoxifen in patients with newly diagnosed ER-positive, HER2-negative breast cancer. pCR will be defined as the absence of residual invasive and in situ cancer on hematoxylin and eosin evaluation of the complete resected breast specimen and all sampled regional lymph nodes following completion of neoadjuvant systemic therapy (i.e., ypT0 ypN0 in the current American Joint Committee on Cancer staging system).
- To evaluate the preoperative endocrine prognostic index score after treatment with TAK-228 plus tamoxifen in patients with newly diagnosed ER-positive, HER2-negative breast cancer.
- To assess the toxicity and safety of TAK-228 plus tamoxifen in patients with newly diagnosed ER-positive, HER2-negative breast cancer.

Exploratory

- To determine the plasma pharmacokinetics of the TAK-228 plus tamoxifen combination.
- To assess the correlation between pCR to TAK-228 plus tamoxifen and changes in Ki67, p53/p63/p73, phosphatidylinositol 3-kinase (PI3K)/protein kinase B (AKT)/mTOR, and NFkB pathways in ER-positive, HER2-negative breast tumors.
- To assess tumor mutational status to identify predictors of response to the TAK-228 plus tamoxifen combination.
- To evaluate Oncotype DX recurrence score before and after treatment with TAK-228 plus tamoxifen.

**Overview of Study Design:**

This open label phase II trial is designed to determine the efficacy and safety of TAK-228 plus tamoxifen in patients with newly diagnosed ER-positive, HER2-negative breast cancer. TAK-228 (30 mg weekly [QW]) plus tamoxifen (20 mg daily [QD]) will be orally (p.o.) administered for 16 weeks. The treatment scheme is shown below. Dose adjustments for TAK-228-associated toxicities will be made based on previous literature. Baseline assessment, prespecified visits, and follow-up visit will be conducted as described below.

[figure not shown]
To evaluate the efficacy of the study treatment, Ki67 will be measured pre- and post-treatment, with the expectation of a post-treatment reduction. Based on prior data for Ki67 changes in the tamoxifen only arm of the IMPACT trial, we will assume null and alternative hypotheses of 60% and 80% reduction in Ki67, respectively. Transformations of the geometric mean and 95% confidence interval will be employed to obtain mean and standard deviation estimates.

**Study Population:**

Patients with newly diagnosed ER-positive, HER2-negative breast cancer. Patients ineligible for inclusion are those with metastatic disease; those previously treated with hormonal therapy (tamoxifen, aromatase inhibitor) or PI3K, AKT, dual PI3K/mTOR, TORC1/2, or TORC1 inhibitors; and those with known hypersensitivity to

tamoxifen or mTOR inhibitors.

**Duration of Study:** 16 weeks.

**FIGURE 1 STUDY OVERVIEW DIAGRAM**

**TABLE 1 SCHEDULE OF EVENTS**

Visit	Screening a	Baseline b	V1	V2	V3	V4	V5	V6	V7*	EOT
Week	-4 to -3	-2 to -1	1	3	4	6	8	12	16*	
Informed Consent	X									
Inclusion/Exclusion	X									
Demographics	X									
Medical History	X									
Physical Exam c		X	X	X	X	X	X	X	X	X
Height	X									
Weight	X	X	X	X	X	X	X	X	X	X
ECOG PS	X	X	X	X	X	X	X	X	X	X
Vital Signs d	X	X	X	X	X	X	X	X	X	X
12-Lead ECG e		X								X
Hematology f		X	X	X	X	X	X	X	X	X
Clinical Chemistry g		X	X	X	X	X	X	X	X	X
FSH/LH/Estradiol h		X								
Serum Pregnancy ( $\beta$ -hCG) i		X								
Urinalysis j		X	X	X	X	X	X	X	X	X
Fasting Lipid Panel k		X			X		X	X	X	X
Bilateral Mammogram and US l		X								X
Breast MRI m		X								X
Clinical Breast Exam		X			X		X	X	X	X
Concomitant Therapies										Continuous from screening period
Tumor Assessments (RECIST 1:1)		X								X
Biopsy n		X					X			
Tumor Tissue o		X				X				
TAK-228 Administration p										Weekly from day 1, week 1 through day 1, week 16
Tamoxifen Administration p										Continuous daily from day 1, week 1 through day 7, week 16
AEs and SAEs										From ICF signing up to and including 30 days after local treatment q
Pharmacokinetics r										Days 1 and 15

Abbreviations: AE = adverse event; ALT = alanine transaminase; ANC = absolute neutrophil count; aPTT = activated partial thromboplastin time; ASP = aspartate transaminase;  $\beta$ -hCG = beta-human chorionic gonadotropin; CBC = complete blood count; ECG = electrocardiogram; ECOG PS = Eastern Cooperative Oncology Group performance status (see Appendix A); EOT = end of treatment; FBG = fasting blood glucose; FSH = follicle stimulating hormone; HbA1c = hemoglobin A1c; HDL-C = high-density lipoprotein cholesterol; ICF = informed consent form; INR = international normalized ratio; LDL-C = low-density lipoprotein cholesterol; LH = luteinizing hormone; MRI = magnetic resonance imaging; p.o. = orally; PT = prothrombin time; QD = daily; QW = weekly; RECIST = Response Evaluation Criteria in Solid Tumors; SAE = serious adverse event; SOC = standard of care; US = ultrasound; V = visit; WBC = white blood cell. Tests and procedures should be done on schedule, but V windows of  $\pm$  4 days are allowed (except as otherwise specified) occasionally for holidays, vacations, and other administrative reasons or if extenuating circumstances prevent a patient from beginning treatment or completing a scheduled assessment within this time frame. Patients will receive surgery within 30 days of the final dose of study treatment. EOT is defined as 7 to 10 days after the final dose of study treatment.

- a. Within 28 days prior to the week 1, day 1 dose of TAK-228 plus tamoxifen.
- b. Within 7 days prior to the week 1, day 1 dose of TAK-228 plus tamoxifen. Only screening procedures not performed within 7 days of dosing are required at baseline.
- c. The baseline symptom-directed medical history and physical examination are not required if the screening medical history and physical examination were conducted within 3 to 7 days prior to week 1, day 1.
- d. Vital sign (blood pressure, heart rate, and oral or temporal temperature) measurements will be obtained during screening, at baseline, and before every V.
- e. A 12-lead ECG will be performed at baseline, at EOT, and when clinically indicated.
- f. A blood sample for CBC with platelet count and differential WBC count will be obtained at baseline; every V [ $\pm$  1 day]; at EOT; and when clinically indicated. If a patient is found to have an ANC <500/mm^3, platelet count < 25,000/mm^3, or both, the CBC with differential should be repeated at least every other day until the ANC and platelet count have exceeded these values.
- g. A blood sample for the clinical chemistry panel (albumin, sodium, potassium, carbon dioxide, chloride, blood urea nitrogen, creatinine, total bilirubin, alkaline phosphatase, AST, and ALT) and evaluation of magnesium, uric acid, and lactate dehydrogenase will be obtained at baseline; every V [ $\pm$  1 day]; at EOT; and when clinically indicated. Fasting serum glucose is to be repeated every week for the length of the study and during follow-up. In-home daily glucose monitoring will be performed by the patients. All patients will be given a glucometer to monitor their daily FBG levels at home. FBG level should be measured after at least 8 hours of fasting. On scheduled TAK-228 dosing days, FBG will be measured before TAK-228 dose. Patients with any abnormal readings (i.e.,  $\geq$  150 mg/dL) will be instructed to notify the study staff immediately for further instructions on the management of their hyperglycemia. Hyperglycemia observed during home glucose monitoring should be confirmed in the clinic. Investigators will be responsible for reviewing the home glucose monitoring logs for hyperglycemia. If no irregularities in the FBG level are observed during a minimum of 2 consecutive months, then the frequency of home fasting glucose testing can be reduced to a minimum frequency of once weekly, depending on the investigator's judgment and approval. Patients will continue to notify the investigator of FBG levels that exceed 150 mg/dL and, if blood glucose levels are not well-controlled or the patient requires either oral hypoglycemic agents or insulin to control blood glucose levels, then the frequency of home testing of FBG levels will be reinstated to daily. HbA1c level will be measured at screening, week 8, and EOT. Coagulation parameters (PT/INR and aPTT) will be measured at baseline, every V, and EOT.
- h. FSH/LH/Estradiol will be measured in all patients at baseline.
- i. For women of childbearing potential, the results of a serum  $\beta$ -hCG pregnancy test must be negative within 7 days before the first treatment dose is administered. If the screening serum  $\beta$ -hCG pregnancy test is performed more than 7 days before dosing, it must be repeated at baseline, with results known to be negative prior to administration of the first dose of the study drugs.  $\beta$ -hCG pregnancy testing is to be repeated as clinically indicated.
- j. Urinalysis will be performed at baseline, every V, and EOT.
- k. A fasting lipid panel will be obtained at baseline; week 4, 8, 12, and 16 of treatment; and EOT. This panel includes total cholesterol, HDL-C, LDL-C, and triglycerides.
- l. Bilateral mammogram and US will be performed at baseline and EOT. **NOTE:** Bilateral mammogram and US performed as SOC can be used for screening/baseline if performed within 90 days prior to the week 1, day 1 dose of TAK-228 plus tamoxifen.
- m. Breast MRI will be performed at baseline and EOT. **NOTE:** Breast MRI performed as SOC can be used for screening/baseline if performed within 60 days prior to the week 1, day 1 dose of TAK-228 plus tamoxifen.
- n. In patients with accessible tumor, biopsies will be conducted at baseline and week 6 of treatment, and if the patient progresses while on treatment, before the patient starts the new treatment.
- o. Banked tumor tissue obtained as part of the patient's standard care and additional biopsies will be evaluated at a later time to determine the correlation of specific molecular markers (ER; Ki67; mitotic index; apoptosis; levels of S6K, 4EBP-1, EIF4E, EIF4G, and EIF4A; levels of phosphorylated S6K, p53, p63, and p73; and p73 and p63 gene signatures) with clinical parameters such as tumor response. These correlative studies will help define a biomarker signature associated with p63/p73 and/or PI3K/AKT dependence and NFkB in ER-positive breast cancers as well as identify new therapeutic options for this group of patients. Tumor mutational analysis will also be performed to identify predictors of treatment response. Oncotype DX testing will also be performed on biopsy and surgical tissue samples.
- p. TAK-228 30 mg p.o. QW for 16 weeks plus tamoxifen 20 mg p.o. QD for 16 weeks. Adjust dose accordingly with Dose Level (see TAK-228 dose modifications).
- q. AEs and SAEs will be captured from the time of ICF signing up to and including 30 days after local treatment. Study treatment-related SAEs that occur beyond 30 days after local treatment and any study patient death should also be reported.
- r. Blood samples for PK analysis will be obtained 1 hour ( $\pm$  15 minutes) before TAK-228 dosing and 1 hour ( $\pm$  5 minutes) after TAK-228 dosing on days 1 and 15. Collect blood samples (10 ml per sampling timepoint) and batch the **plasma** for future analyses.

\*Patients will be treated until completion of 16 weeks.

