### 2.4 Toxicology

The toxicologic profiles obtained in the Good Laboratory Practice (GLP)-compliant and non-GLP-compliant studies in rats and monkeys were generally consistent with pharmacologic inhibition of mTORC1/2 activity.

The findings in rat and monkey repeat-dose toxicology studies with TAK-228, including bone marrow and lymphoid depletion; gastrointestinal (GI), liver, pancreas, and skin effects; and effects on glucose and insulin levels, can be monitored in clinical trials. The toxicities seen in the repeat-dose toxicology studies, such as GI effects and glucose and insulin increases, are consistent with the treatment-emergent adverse

events (TEAEs), including mucositis and hyperglycemia, observed to date in patients receiving TAK-228. Rat and rabbit range-finding embryo-fetal studies demonstrated teratogenic, fetotoxic, and abortive effects with TAK-228. TAK-228 does not present a genotoxic risk and was negative for phototoxicity in the 3T3 fibroblast assay.

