### 3.2 Safety

Among the 438 patients who had received  $\geq$ 1dose of study drug as of the clinical data cutoff date (09 December 2015), 20 deaths had occurred within 30 days of the last dose. Of these fatal events, 1 death (ventricular fibrillation and cardiac arrest in Study INK128-001) was considered related to TAK-228 treatment.

Across the studies and regardless of causality or dosing regimen, the most common TEAEs included nausea, fatigue, hyperglycemia, vomiting, diarrhea, stomatitis, and decreased appetite.

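### No pregnancy test is scheduled once dosing starts, leaving up to 118 days to the last tamoxifen dose; assays at weeks 4, 8 and 12 on blood already drawn would cut the longest untested interval to 34 days

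*Combined protocol and SAP*

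**What the plan says.** Women of childbearing potential are eligible (section 10.1, criterion 5). Table 1 marks serum beta-hCG at baseline only. Footnote i and inclusion criterion 10 require a negative result within 7 days before the first dose, and footnote i then says that "pregnancy testing is to be repeated as clinically indicated". Neither the contraception text in section 11.5 nor the pregnancy-reporting text in section 14.3 adds a scheduled test.

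Table 1 gives TAK-228 "Weekly from day 1, week 1 through day 1, week 16" and tamoxifen "Continuous daily from day 1, week 1 through day 7, week 16".

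On fetal risk, section 2.4 states: "Rat and rabbit range-finding embryo-fetal studies demonstrated teratogenic, fetotoxic, and abortive effects with TAK-228". Section 11.5 adds that the effects of TAK-228 on human pregnancy are unknown. Section 5 places tamoxifen in FDA Pregnancy Category D, with human evidence of fetal risk.

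Four controls are in place:
- Two contraceptive methods used together, or true abstinence (sections 10.1 and 11.5).
- Visits with physical examination at weeks 1, 3, 4, 6, 8, 12 and 16 (Table 1).
- A duty to inform the investigator and stop both drugs once the patient is, or suspects that she is, pregnant (section 14.3).
- Guidance in section 5 that women of childbearing potential should begin tamoxifen during menstruation, use barrier or non-hormonal contraception, and avoid pregnancy for 2 months after stopping.

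**The concern.** The stopping rule in section 14.3 works only once a pregnancy is known or suspected. Contraception lowers the chance of pregnancy but does not detect one. That leaves the clinical prompt for a repeat test, and it may be weaker than usual here. Section 5 says that tamoxifen can make menstruation light or infrequent, or stop it, so a missed period is a less specific sign. Section 3.2 reports that, with TAK-228, "the most common TEAEs included nausea, fatigue, hyperglycemia, vomiting, diarrhea, stomatitis, and decreased appetite", so early symptoms of pregnancy could be put down to the drug.

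What is at stake is how long an unrecognised pregnancy would be exposed to two drugs for which the protocol describes fetal risk. The primary Ki67 analysis, the pCR analysis and the safety summaries are not affected.

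**Working it through.** The documents give no figure for this interval, so there is none to reproduce. What follows is calendar arithmetic.

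**Inputs.** First dose at t = 0. Earliest permitted test at t = −7 (footnote i). Last TAK-228 dose on week 16, day 1: t = 15 × 7 = 105. Last tamoxifen dose on week 16, day 7: t = 105 + 6 = 111, which makes 112 dosing days, or 16 weeks, as stated. Assumption: each visit falls on day 1 of its named week, so weeks 4, 8, 12 and 16 are t = 21, 49, 77 and 105.

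**Interval with no scheduled test, as planned.**
- To the last tamoxifen dose: 7 + 111 = 118 days.
- To the last TAK-228 dose: 7 + 105 = 112 days, or 113 if that dose uses the ±1-day window in section 11.1.

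**With tests at weeks 4, 8 and 12.** The gaps are 21 − (−7) = 28, 49 − 21 = 28, 77 − 49 = 28, and 111 − 77 = 34. The longest is 34 days. If the week 12 draw is one day early, as footnotes f and g allow, it is 34 + 1 = 35. Among all choices of existing visits, the best single visit leaves 62 days, the best pair 42 and the best three 34.

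**With week 16 added.** The gaps are 28, 28, 28, 28 and 111 − 105 = 6. The longest is 28 days nominal, or 28 + 2 = 30 when adjacent draws move one day in opposite directions. Section 11.1 has TAK-228 taken in the morning of day 1. If the final dose is counted as taken before the week 16 result is known, that test prevents no TAK-228 dose and at most the 6 tamoxifen doses of days 2 to 7.

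**End-of-treatment test instead.** Table 1 says "EOT is defined as 7 to 10 days after the final dose of study treatment", so t = 118 to 121. Moving the fourth test there would leave 118 − 77 = 41 to 121 − 77 = 44 days between tests, and it shortens no planned dosing.

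**Longest dosing after conception.** Assumptions: nothing else prompts a test, visits are nominal, and the assay turns positive 10 to 14 days after conception. A pregnancy just missed at one test then continues to the next test or the last dose, so the maximum is the longest gap plus the assay lag.

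| Schedule | Calculation | Longest dosing after conception |
|---|---|---|
| As planned, conception on or before the first dose | all dosing days | 112 days |
| As planned, treatment started during menses, no conception before t = 10 to 14 (assumption) | 111 − 14 to 111 − 10 | about 97 to 101 days |
| Weeks 4, 8, 12 | 34 + 10 to 34 + 14 | 44 to 48 days |
| Weeks 4, 8, 12, 16 | 28 + 10 to 28 + 14 | 38 to 42 days |

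**Expected pregnancies.** The number of women of childbearing potential and the contraceptive failure rate are not in the documents. With 5 to 15 women and 1% to 6% failure per year, both assumed, the product runs from 5 × 0.01 × 118/365 = 0.016 to 15 × 0.06 × 118/365 = 0.29. The upper end multiplies two assumed maxima, and 6% is hard to reconcile with two concurrent methods. At 1%, 15 women give 15 × 0.01 × 118/365 = 0.05. These figures show only that the number is well below one.

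**The case against.** The strongest reply is that the plan contains no error. Footnote i states a complete rule, Table 1 and criterion 10 agree with it, and nothing in the protocol promises testing during treatment. That stands: this is an improvement to a stated rule, and the documents do not support calling it a breach or an omission of something promised.

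A second reply is that the controls already in place make an exposed pregnancy unlikely. Patients are seen at seven treatment visits, and suspicion alone stops both drugs. The section 5 advice to begin tamoxifen during menstruation also makes conception around the first dose improbable, which is why the present worst case is given as a range from about 97 to 112 days. That advice is background guidance: it is neither an eligibility criterion nor part of the administration instructions in section 11.1, so it narrows the range without settling it. None of these controls is a scheduled means of detection.

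A third reply is that weaker clinical prompts are an inference. That also stands. The documents give no rate of menstrual change, and nausea or a missed period could equally lead an investigator to order a test. A reader might infer that pregnancies would go unnoticed for the whole course; the documents do not show that. The 118 days is the longest interval without a scheduled test, and testing on clinical indication remains open throughout.

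Two further readings should be resisted. The 28-day figure might suggest that four tests are needed, but the fourth adds little. The general ±4-day visit window might be used to lengthen the intervals, but it applies only where nothing else is specified, and footnotes f and g set ±1 day for the draws that would be used.

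**Conclusion.** The point holds as a low-cost patient-safety improvement. Serum beta-hCG is scheduled only before dosing, which leaves up to 118 days to the last tamoxifen dose and 112 (113 with the dosing window) to the last TAK-228 dose. Tests at weeks 4, 8 and 12 reduce the longest untested interval during dosing to 34 days nominal and carry most of the benefit; week 16 is optional.

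The intervals rest on visits falling on day 1 of the named week. The reduction in worst-case exposure, from about 97 to 112 days down to 44 to 48 (or 38 to 42 with week 16), also rests on an assumed assay lag of 10 to 14 days and on no other prompt for a test. It describes one unrecognised pregnancy. It should not be read as a prediction that one will occur, because the documents do not supply the inputs for such an estimate.

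**What to change.** In Table 1 and footnote i, for women of childbearing potential, add serum beta-hCG at weeks 4, 8 and 12 and keep repeats on clinical indication. Week 16 may be added if a 28-day maximum is wanted. An end-of-treatment test would serve follow-up only. If the menstruation-timed start of tamoxifen is meant as a safeguard, a sentence in section 11.1 would make it operative.

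No new visit or draw should be needed. Footnote f already states "A blood sample for CBC with platelet count and differential WBC count will be obtained at baseline; every V", footnote g does the same for chemistry, and footnote k states "A fasting lipid panel will be obtained at baseline; week 4, 8, 12, and 16 of treatment; and EOT". This assumes that the laboratory can add the assay to a sample already taken.

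The cost is three assays per woman of childbearing potential, or four with week 16. With an assumed 5 to 15 such women, that is 3 × 5 = 15 to 3 × 15 = 45 assays, or 4 × 5 = 20 to 4 × 15 = 60. The downside is an occasional false positive to follow up.

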## LIST OF ABBREVIATIONS

Abbreviation	Term
AE	adverse event
AI	aromatase inhibitor
AKT	protein kinase B
ALT	alanine aminotransferase
ANC	absolute neutrophil count
API	active pharmaceutical ingredient
AST	aspartate aminotransferase
AUC	area under the curve
C max	maximum plasma concentration
CBR	clinical benefit rate
CI	confidence interval
CR	complete response
CRF	case report form
CTCAE	Common Terminology Criteria for Adverse Events
CYP	cytochrome P 450
DDI	drug-drug interaction
DLT	dose-limiting toxicity
ECG	electrocardiogram
4EBP-1	eukaryotic translation initiation factor 4E binding protein-1
EIF	eukaryotic translation initiation factor
ER	estrogen receptor
EOT	end of treatment
FBG	fasting blood glucose
FDA	Food and Drug Administration
FSG	fasting serum glucose
GI	gastrointestinal
GLP	Good Laboratory Practice
HbA1c	glycosylated hemoglobin
HER2	human epidermal growth factor receptor 2
HR	hazard ratio
IB	investigator brochure

Abbreviation	Term
ICF	informed consent form
IC50	half-maximal inhibitory concentration
IHC	immunohistochemical
IV	intravenous
mBC	metastatic breast cancer
MM	multiple myeloma
MTD	maximum tolerated dose
mTOR	mammalian target of rapamycin
mTORC	mammalian target of rapamycin complex
NCI	National Cancer Institute
NHL	non-Hodgkin Lymphoma
OCT	organic cation transporter
PAX2	paired box 2
pCR	pathological complete response
PD	progressive disease
PEPI	preoperative endocrine prognostic index
PFS	progression-free survival
PI3K	phosphatidylinositol 3-kinase
PK	pharmacokinetics
p.o.	per os; by mouth (orally)
PPI	protein pump inhibitor
PR	partial response
QD	once daily
QD×3 days per week	once daily for 3 consecutive days followed by a 4-day dosing holiday every week
QD×5 days per week	once daily for 5 consecutive days followed by a 2-day dosing holiday every week
QTc	heart rate-corrected QT interval
QW	once weekly
RECIST	Response Evaluation Criteria in Solid Tumors
RP2D	recommended phase II dose
S6K1	ribosomal protein S6 kinase 1
SAE	serious adverse event
SD	stable disease
SSRI	selective serotonin reuptake inhibitor
tmax	time to reach Cmax

Abbreviation	Term
TEAE	treatment-emergent adverse event
TPP	time to progression
ULN	upper limit of normal
US	ultrasound
WM	Waldenström's macroglobulinemia

